If the patient meets all of the criteria above, and agrees to continue with additional treatment of ¹⁷⁷Lu-PSMA-617, the investigator may administer a further 2 cycles. A maximum of 6 cycles of radioligand therapy is allowed. If the patient does not meet any of the criteria or does not agree to additional ¹⁷⁷Lu-PSMA-617 treatment, then no additional doses of ¹⁷⁷Lu-PSMA-617 will be administered after Cycle 4. After the last cycle of ¹⁷⁷Lu-PSMA-617, patients can continue best supportive/best standard of care alone.

Best supportive/best standard of care for each patient will be selected at the discretion of the patient's physician, prior to randomization and will be administered per the physician's orders and continued until the patient comes off the treatment part of the study and enters the long-term follow-up stage.

A patient may choose to discontinue randomized treatment part of the study at any time.

Before final analysis of alternate primary endpoint OS:

If a patient chooses only to discontinue from the randomized treatment in the study for a reason other than radiographic progression, the patient will be asked to confirm if they consent to continue to be followed for long-term safety, rPFS, and survival follow-up. The patient will continue to be followed for long-term follow-up unless they specifically withdraw consent from long-term follow-up of the study. An End of Treatment (EOT) visit should occur once a patient discontinues randomised treatment for any reason (patient or investigator decision, going on to long-term follow-up, etc.).

The EOT visit should occur approximately 30 days from the last dose of ¹⁷⁷Lu-PSMA-617 or the date of the best supportive/best standard of care end of treatment decision (whichever occurs later), but before the initiation of subsequent anti-cancer treatment, outside of what is allowed on study.

If a patient discontinues randomized treatment for any reason other than radiographic progression, they will be asked for permission to continue collecting radiographic images (bone scans and CT scans and/or MRIs) for the purpose of continuing to assess rPFS.

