If the patient meets all of the criteria above, and agrees to continue with additional treatment of ¹⁷⁷Lu-PSMA-617, the investigator may administer a further 2 cycles. A maximum of 6 cycles of radioligand therapy is allowed. If the patient does not meet any of the criteria or does not agree to additional ¹⁷⁷Lu-PSMA-617 treatment, then no additional doses of ¹⁷⁷Lu-PSMA-617 will be administered after Cycle 4. After the last cycle of ¹⁷⁷Lu-PSMA-617, patients can continue BSC/BSoC alone.

BSC/BSoC for each patient will be selected at the discretion of the patient's physician, prior to randomization and will be administered per the physician's orders and continued until the patient comes off the treatment part of the study and enters the long-term follow-up stage.

A patient may choose to discontinue the randomized treatment part of the study at any time. If a patient chooses only to discontinue from the randomized treatment in the study for a reason other than radiographic progression, the patient will be asked to confirm if they consent to continue to be followed for long term safety, radiographic Progression-Free Survival (rPFS), and survival follow up. The patient will continue to be followed for long term follow up unless they specifically withdraw consent from long term follow-up of the study. Crossover to ¹⁷⁷Lu-PSMA-617 treatment is not allowed.

An End of Treatment (EOT) visit should occur once a patient discontinues randomized treatment for any reason (patient or investigator decision, going on to long term follow up, etc.). The EOT visit should occur approximately 30 days from the last dose of ¹⁷⁷Lu PSMA-617 or the date of the best supportive/best standard of care end of treatment decision (whichever is later), but before the initiation of subsequent anti-cancer treatment, outside of what is allowed on study.

After the EOT visit, patients will enter the long-term follow-up period. The long-term follow-up period will include the collection of rPFS (if discontinuing for reasons other than radiographic progression), survival and information about new treatments, along with the patient's response to these treatments, adverse events assessment, and results of hematology and chemistry testing. During follow-up, patients will be followed for safety and survival. They will be contacted every 3 months (± 1 month) via phone, email, or letter for up to 24 months or until 508 deaths have occurred, whichever is sooner.

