8.1.1 Primary Efficacy Definitions

Overall Survival (OS) (months): $(\text{Date of death/censor} - \text{Date of randomization} + 1) / 30.4375$. OS is defined as the time (in months) from the date of randomization to the date of death due to any cause. If the patient is not known to have died, then OS will be censored. The censoring date is date of last contact (see Section 5), i.e. the date the patient was last known to be alive).

Radiographic progression-free survival (rPFS) (months): $(\text{Date of radiographic PD/death/censor} - \text{date of randomization} + 1) / 30.4375$. rPFS is defined as the time (in months) from the date of randomization to the date of radiographic disease progression as outlined in PCWG3 Guidelines (Scher et al 2016; protocol Appendix 7, RECIST v1.1; FDA guidance, 2007; EMA guideline, 2012) or death due to any cause.

- Note:
 - In the investigational treatment arm, a patient continues to be in the treatment period of the study on BSC/BSoC after receiving their final dose of ¹⁷⁷Lu-PSMA-617.

- Patients are at risk of the different types of rPFS events for different lengths of time:
 - RECIST v1.1 (Soft tissue) PD can occur up through last scan, which can be during long term follow-up (LTFU).
 - Bone PD can occur up to scan prior to last scan (with confirmation at last scan), which can be during LTFU.
 - Death can occur up through 24 weeks past the last study scan, or if no post treatment scans, up to 24 weeks after the first randomized treatment dose (based on the 2 missed visits censoring rule)
- Date of radiographic progressive disease (radiographic PD) event: date of the first CT/MRI/bone scan PD/death due to any cause occurs with no more than 1 immediately prior missing assessment.
 - RECIST 1.1 PD
 - Assessment in which Overall RECIST v1.1 Response is PD
 - Date of PD is date of first appearance of the new lesion(s), if applicable.
 - Bone scan PD must be confirmed as follows (rules allow for a flare effect at the first post-treatment scan). See examples in Appendix B:
 - Rule 1 (Progression at week 8 confirmed at week 16): If there are at least two new lesions on the first post-treatment scan, they must be confirmed with at least two additional lesions on the next scan (2+2 rule). The date of progression is the date of the first post-treatment scan.

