 - Rule 2 (Progression at week 16 or later confirmed at next scan): For scans after the first post-treatment scan, there must be at least two new lesions relative to the first post-treatment scan (treating as a new baseline) that remain persistent (confirmed) on a subsequent scan. The date of progression is the date of the scan that first documents the second lesion compared to first post-treatment scan.
- Date of Censoring for rPFS:
 - The censoring date is the date when the last evaluable radiographic assessment (CT/MRI/bone scan) determined a lack of progression.
 - If there were no evaluable assessments, censoring occurs at the date of randomization.
 - Patients who have 2 or more consecutive missed tumor assessments immediately prior to progressive disease (PD) or death will be censored at the date of the last evaluable tumor assessment prior to those missing tumor assessments. Study scans are every 8 weeks +/- 4 days for the first 24 weeks, then every 12 weeks +/- 4 days and are scheduled relative to date of first dose of randomized treatment. Thus, subjects are considered as having 2 missed assessments if:
 - $\text{day } 117 \leq \text{study day of event scan} \leq \text{day } 229$ and time since last evaluable assessment ≥ 118 days
(2 missed visits, $117 = 16 \text{ weeks} + 4 \text{ days} + 1$; $229 = 24 \text{ weeks} + 8 \text{ weeks} + 4 \text{ days} + 1$)
 - $\text{day } 230 \leq \text{study day of event scan} \leq \text{day } 313$ and time since last evaluable assessment ≥ 146 days

(2 missed visits, 145 = 20 weeks + 4 days + 1; 313 = 24 weeks + 20 weeks + 4 days +1)

- study day of event scan \geq day 314 and time since last evaluable assessment \geq 174 days

(2 missed visits, 173 = 24 weeks + 4 days + 1)

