First Sensitivity analysis of rPFS: This sensitivity analysis is the same as the primary rPFS analysis (Section 8.1.1) except with additional rPFS events as follows:

- Includes events regardless of intervening missed assessments.
- Bone PDs are indicated by one of the following per PCWG3 guidelines:
 - Rule 1 (Progression at week 8 and confirmed at week 16): same as Rule 1 described in Section 8.1.1.
 - Modified Rule 2 (Progression at week 16 or later without confirmation): PD can still only occur at the second post treatment scan or later. The date of bone PD is the date when there are at least two new lesions relative to the first post-treatment scan without confirmation.
- Includes all radiographic PD and deaths captured in the study, including scans not centrally read that are captured on the LTFU CRF page.

This sensitivity analysis will use the PFS-FAS population and will compare the two treatment arms using the same analysis conventions described in Section 8.2.1.

Second Sensitivity analysis: This sensitivity analysis is the same as the primary rPFS analysis except with additional censoring as follows:

- Deaths occurring after start of a new anti-cancer therapy will be censored at start date of new therapy.

This sensitivity analysis will use the PFS-FAS population and will compare the two treatment arms using the same analysis conventions described in Section 8.2.1.

Third Sensitivity analysis: This sensitivity analysis is the same as the primary rPFS analysis except rPFS will be defined from the date of first dose of randomized treatment. This sensitivity analysis will use the PFS-FAS population and will compare the two treatment arms using the same analysis conventions described in Section 8.2.1.

Fourth Sensitivity analysis: This sensitivity analysis is the same as the primary rPFS analysis except using local investigator assessments. This sensitivity analysis will use the PFS-FAS population and will compare the two treatment arms using the same analysis conventions described in Section 8.2.1.

Sensitivity analyses to assess the impact of COVID-19:

The impact of missing PCWG3 (bone scans) and/or RECIST assessments on the primary rPFS analysis caused by COVID-19 will be evaluated by the existing first sensitivity analysis.

The following analyses of rPFS will be used to estimate the treatment effect in the absence of the COVID-19 virus:

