- Analysis as per the primary rPFS analysis but censoring COVID-19 related deaths at the last adequate assessment prior to the death.
- An analysis as per the 'first sensitivity analysis' but censoring COVID-19 related deaths at the date of death.

For the analyses above, the patients with COVID-19 related deaths will be determined in a blinded fashion by clinical review of the data and will be documented prior to database lock.

The same analyses conventions used for the primary analyses of rPFS, as described in section 8.2.1, will be performed (without p-values).

Supportive analyses of rPFS:

rPFS will be derived in all patients randomized (FAS population) using the same conventions as described in Section 8.1.1 but will consider patients randomized before March 5, 2019 who withdrew consent from the study (i.e. no further data on radiographic progression is available) as (1) censored at time of withdrawal and (2) a rPFS event at the time of withdrawal.

The following data will be summarized using the FAS:

- (1): Number (%) rPFS events (radiographic PD, deaths) and censored, reason censored (ongoing without event, withdrew consent, event documented with two or more missed tumor assessments, adequate assessment not available)
- (2): Number (%) rPFS events (radiographic PD, deaths, withdrew consent) and censored, reason censored (ongoing without event, withdrew consent, event documented with two or more missed tumor assessments, adequate assessment not available)

Missing tumor assessments: The number of patients with at least one missing/not evaluable tumor assessment (TA) based on independent central review will be presented together with the following breakdown categories: number of patients with 1, 2, 3, 4, 5, >5 missing/not evaluable TAs. The purpose of this analysis is to gain an insight as to whether the TAs have been carried out in accordance with the protocol and to understand if any meaningful discrepancies exist between the pattern of missing assessments by treatment arms. Timing of all tumor assessments will be depicted graphically and displayed by treatment arm.

Since the planned tumor assessments are every 8 weeks in the first 24 weeks from C1D1 and every 12 weeks thereafter, the following time windows (in weeks) will be constructed for each patient from the date of randomization: (note the open parenthesis such as (12, 20] indicates that week 12 doesn't belong to this interval and week 12+1 day belongs to that interval)

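### The second rPFS sensitivity analysis censors patients at new anti-cancer therapy only if they later die, so its hazard ratio can shift whenever therapy rates differ by arm

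*SAP*

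**What the plan says.** SAP 8.2.1 introduces the second sensitivity analysis with "This sensitivity analysis is the same as the primary rPFS analysis except with additional censoring as follows" and gives one rule: "Deaths occurring after start of a new anti-cancer therapy will be censored at start date of new therapy". Everything else follows the primary definition in SAP 8.1.1, which has no rule for new therapy. Three things follow.

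- **Progression after new therapy stays an event.** Such progressions can be seen. Long-term follow-up includes "collection of rPFS (if discontinuing for reasons other than radiographic progression), survival and information about new treatments" (SAP 3.1). Patients who stop treatment for other reasons are asked to keep having scans: "they will be asked for permission to continue collecting radiographic images" (Protocol 3.1). SAP 8.1.1 allows both soft-tissue and bone progression to be dated during long-term follow-up.
- **A patient with neither event keeps the primary rule:** "The censoring date is the date when the last evaluable radiographic assessment (CT/MRI/bone scan) determined a lack of progression".
- **Deaths well after the last scan count in the primary analysis:** "Death can occur up through 24 weeks past the last study scan" (SAP 8.1.1). These are the deaths that the second analysis can remove.

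No other rPFS sensitivity analysis deals with subsequent therapy. The others address missed or unconfirmed assessments, the time origin, local reading and COVID-19. The planned list of reasons for rPFS censoring has no entry for new therapy. SAP 9.8 tabulates post-treatment therapy in the FAS but does not link it to progression status.

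**The concern.** Take three patients who start new therapy on the same day without progression. The first later dies and is censored on that day. The second later progresses and is an event. The third does neither and stays at risk until the last scan. On the day of censoring nothing distinguishes them. The first leaves the risk set only because of what happens afterwards.

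That breaks the condition for ordinary censoring, namely that those removed are represented by those who stay. Deaths are taken out of the post-therapy period while event-free survivors still contribute follow-up, so the counted event rate after therapy is too low. If the arms start new therapy at different rates, the deficit differs by arm and the hazard ratio moves. A reader comparing this analysis with the primary could take that movement for an effect of later therapy, or could miss a real effect that it masks.

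**Working it through.** **1. The plan's own figure.** The inputs are in SAP 3.4 and 3.1: 364 events, HR 0.67 (medians 4 and 6 months), one-sided alpha 0.004, 2:1 allocation.

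- Power = Φ(√(D·p(1−p))·|ln HR| − z), with √(364 × 2/9) = 8.994 and z = 2.652.
- HR 0.67: 8.994 × 0.4005 − 2.652 = 0.950, so power is 82.9%.
- HR 4/6: 8.994 × 0.4055 − 2.652 = 0.995, so power is 84.0%.
- Critical HR: exp(−2.652/8.994) = 0.745.

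The stated 84% and 0.745 reproduce. Neither depends on the rule at issue.

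**2. Illustration.** The documents give no rate of new therapy, so its effect can only be shown under assumptions.

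- Taken from the plan: 557 patients, 2:1 allocation, medians 4 and 6 months, at least 6 months of follow-up, scans at weeks 8, 16 and 24 and then every 12 weeks.
- Assumed: exponential times; deaths are 20% or 35% of the rPFS hazard; new therapy starts at 0.03 to 0.10 per month, unrelated to prognosis and without effect; accrual is uniform over 8 months; every patient keeps being scanned.
- Not modelled: the rule on two missed assessments.
- Size: 557 × 400 = 222,800 simulated patients per row, counts scaled back to 557, unstratified Cox HR.

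Planned effect:

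| Death share | Therapy per month, control / active | Progressions / deaths after therapy | HR, primary | HR, SAP rule | HR, all censored at therapy start |
|---|---|---|---|---|---|
| 0.20 | 0.05 / 0.05 | 57 / 16 | 0.670 | 0.667 | 0.672 |
| 0.20 | 0.10 / 0.03 | 59 / 16 | 0.667 | 0.679 | 0.667 |
| 0.20 | 0.03 / 0.10 | 77 / 21 | 0.672 | 0.652 | 0.670 |
| 0.35 | 0.05 / 0.05 | 46 / 26 | 0.667 | 0.660 | 0.663 |
| 0.35 | 0.10 / 0.03 | 47 / 28 | 0.673 | 0.695 | 0.673 |
| 0.35 | 0.03 / 0.10 | 60 / 35 | 0.672 | 0.637 | 0.672 |

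No treatment effect (both medians 4 months), unequal therapy rates:

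| Death share | Therapy per month, control / active | HR, primary | HR, SAP rule | HR, all censored at therapy start |
|---|---|---|---|---|
| 0.20 | 0.10 / 0.03 | 1.003 | 1.023 | 0.999 |
| 0.20 | 0.03 / 0.10 | 1.002 | 0.981 | 1.003 |
| 0.35 | 0.10 / 0.03 | 1.001 | 1.039 | 1.000 |
| 0.35 | 0.03 / 0.10 | 0.993 | 0.957 | 0.992 |

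**3. Reading the tables.** With equal rates the SAP rule barely moves the HR. With unequal rates it moves up when control starts more therapy and down when the active arm does. The largest shifts are 0.672 − 0.637 = 0.035 under the planned effect and 1.039 − 1.001 = 0.038 under no effect. Against sampling error, ln(0.637/0.672) = −0.053. With 346 events in that row the standard error is 1/√(346 × 2/9) = 0.114, so the shift is about half a standard error. Therapy does nothing in this model, so a sound check should not move. Censoring all such patients at therapy start keeps the HR within 0.004 of the primary in every row of both tables.

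**4. Second run.** Over the same range of therapy rates, a second run gave 0.652 to 0.725 for the SAP rule against 0.678 to 0.702 for the primary, and 0.954 to 1.020 against 0.984 to 0.989 under no effect. Censoring everyone at therapy start stayed within about 0.01 of the primary.

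**The case against.** **The analysis does answer a question.** A reader might infer that it isolates nothing. That goes too far. It changes one element of the primary analysis, so it shows how far the result rests on deaths after new therapy without earlier progression. The question is narrow and the SAP does not state it, but it exists.

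**The date is a choice.** A reader might also infer that censoring at therapy start contradicts the last-scan rule in SAP 8.1.1. That rule defines the primary analysis, and the second analysis departs from it openly. Other secondary rPFS analyses also vary the date. One COVID-19 analysis is described as "censoring COVID-19 related deaths at the last adequate assessment prior to the death", another uses the date of death, and a supportive FAS analysis uses the time of withdrawal. Nor is the date the source of the distortion, since censoring all such patients at therapy start left the HR unchanged.

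**No imbalance is documented.** It is tempting to say that open-label control patients will start new therapy earlier. The documents report early withdrawal of consent in that arm, with remedial measures effective 5 March 2019, and the rPFS analysis set begins on that date. They give no therapy rates for either arm.

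**The retained progressions may be fewer than simulated.** Scans after stopping depend on the patient's permission, and long-term follow-up scans that were not centrally read enter only the first sensitivity analysis.

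All four points stand. None of them removes the dependence of censoring on a later death.

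**Conclusion.** The point holds as a minor one. The outcome-dependent censoring follows from the SAP text and needs no simulation. Its size does rest on assumptions: up to about 0.035 to 0.04 on the HR in the main illustration, in either direction, when therapy rates differ by arm (0.03 against 0.10 per month), and close to nothing when they are equal. A real link between prognosis and the start of therapy was not modelled.

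A reader might infer that the rPFS conclusion is at risk. It is not. SAP 8.2.1 reports nominal p-values for the rPFS sensitivity analyses and draws no inference from them, so the primary test, its alpha and its power are untouched. What is weakened is the one planned rPFS check on subsequent therapy.

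**What to change.** Reword the second sensitivity analysis so that every patient who starts new anti-cancer therapy without prior radiographic progression is censored at the start of that therapy, whether the patient later progresses, dies or has neither event. Report by arm the number so censored.

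If the last evaluable assessment on or before that date is preferred for consistency with SAP 8.1.1, apply it to all such patients. This is the weaker option: with unequal rates it gave 0.630 to 0.718 in the main illustration. Part of that spread depends on how tied events and censorings at a scan date are ordered, so rely on it only as a sign that a shift remains. Do not move only the patients who later have an event to their last scan. That repeats the fault on a larger scale, with HRs of 0.567 to 0.781 in the second run.

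The cost is a few SAP lines, using dates already collected, and some precision in one nominal analysis. In the illustration, events fall from 346–361 under the SAP rule to 279–310. In the row with the fewest events left (death share 0.20, therapy 0.03 / 0.10) they go from 355 to 279, and the standard error of ln HR rises from 1/√(355 × 2/9) = 0.113 to 1/√(279 × 2/9) = 0.127.

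### The rPFS analysis named as the check on scans missed because of COVID-19 changes three rules at once, so its difference from the primary analysis cannot be attributed to missed scans

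*SAP*

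**What the plan says.** The primary rPFS rules are in SAP sections 8.1 and 8.1.1. Progression comes from independent central review. On missed scans: "Patients who have 2 or more consecutive missed tumor assessments immediately prior to progressive disease (PD) or death will be censored", with the censoring date set at the last evaluable assessment before the gap. Under Rule 2, bone progression after the first post-treatment scan needs at least two new lesions "that remain persistent (confirmed) on a subsequent scan".

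SAP section 8.2.1 defines the first sensitivity analysis as the primary analysis with added events from three sources:

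- "Includes events regardless of intervening missed assessments".
- "Modified Rule 2 (Progression at week 16 or later without confirmation): PD can still only occur at the second post treatment scan or later".
- "Includes all radiographic PD and deaths captured in the study, including scans not centrally read that are captured on the LTFU CRF page".

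Under the COVID-19 heading of the same section, the effect of missed bone scans or RECIST assessments "on the primary rPFS analysis caused by COVID-19 will be evaluated by the existing first sensitivity analysis". Two further COVID-19 analyses of rPFS follow. One uses the primary rules with COVID-19 deaths censored. The other uses the first-sensitivity rules "but censoring COVID-19 related deaths at the date of death".

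**The concern.** A sensitivity analysis meant to show what missed scans did to the primary result should differ from the primary analysis in how missed scans are handled, and as little as possible in anything else. This one also relaxes the bone endpoint for all patients and changes the source of some reads.

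If the hazard ratio moves, the cause could be missed scans, unconfirmed bone findings or reads made outside central review. If it does not move, opposite shifts may have cancelled. rPFS can make the trial positive on its own (SAP section 4), so readers will want to know whether its result survives pandemic disruption of imaging. As written, the SAP names an analysis for that question whose result cannot be read as an answer to it.

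**Working it through.** **1. Rules side by side**

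| Feature | Primary (8.1, 8.1.1) | First sensitivity (8.2.1) | Link to missed scans |
|---|---|---|---|
| Event after 2 or more missed assessments | Censored at last evaluable scan | Counts | Direct, whatever the cause of the miss |
| Bone progression from week 16 | Must be confirmed on a later scan | No confirmation needed | Partial: recovers progressions whose confirmatory scan was missed, but also counts those whose next scan was done and did not confirm |
| Source of reads | Central review | Adds follow-up scans not centrally read | Partial: fills gaps in the central data, but with reads from outside central review |

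The SAP does not call the third source local reads. I infer it from section 8.1, which says sites assess imaging locally and enter it in the CRF, and from section 3.2, which says the study is open-label.

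**2. Does another planned rPFS analysis separate these changes?**

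- Second sensitivity analysis: censors deaths after new anti-cancer therapy.
- Third: moves the time origin to first dose.
- Fourth: uses local assessments throughout.
- Two COVID-19 death analyses: change only how those deaths are handled, one on each rule set.
- FAS supportive analyses: concern consent withdrawals before 5 March 2019.

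Planned rPFS analyses that change only the missed-assessment rule: 0. Planned rPFS analyses that use the COVID-19 cause of a missed scan: 0, although SAP section 6.2 sets up deviation categories that include missing efficacy assessments.

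**3. The plan's own figure**

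The point does not depend on the power calculation, but that calculation fixes the hazard-ratio scale. With 364 events, 2:1 allocation and 1-sided alpha 0.004 (SAP 3.4):

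- √(364 × 2/9) = 8.994 and z(0.004) = 2.652.
- Power at HR 4/6: Φ(8.994 × 0.4055 − 2.652) = Φ(0.995) = 84.0%. At HR 0.67 it is 82.9%. The stated 84% is reproduced.
- Critical HR: exp(−2.652/8.994) = 0.745, as stated.

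**4. Can the contrast move when nothing is missed?**

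By logic, yes: changes two and three add events whether or not any scan was missed. A small simulation illustrates it, with 80 trials per scenario, 557 patients, 2:1 allocation and exponential rPFS with medians of 4 and 6 months.

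These inputs are assumed and not in the documents: 20% of events are deaths; follow-up is uniform over 180 to 500 days; unconfirmed bone calls occur at 3% per visit; added local calls occur at 3% per visit in both arms, or at 5% control and 1% active. Added calls start at the second scan. Mean hazard ratios:

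| Scans missed per visit | Local calls (control/active) | Primary | Missed-scan rule only | Bone rule only | Added reads only | All three |
|---|---|---|---|---|---|---|
| 0% | 3% / 3% | 0.688 | 0.688 | 0.709 | 0.708 | 0.726 |
| 0% | 5% / 1% | 0.703 | 0.703 | 0.721 | 0.670 | 0.689 |
| 20% | 3% / 3% | 0.681 | 0.687 | 0.697 | 0.699 | 0.720 |
| 20% | 5% / 1% | 0.684 | 0.691 | 0.704 | 0.654 | 0.681 |

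- With no scan missed, the combined analysis shifts by 0.726 − 0.688 = +0.038, or 0.689 − 0.703 = −0.014.
- With 20% missed and equal local calls, it shifts by +0.039, while the missed-scan rule alone accounts for 0.687 − 0.681 = +0.006.
- With 20% missed and unequal local calls, it shifts by −0.003, while the missed-scan rule alone gives 0.691 − 0.684 = +0.007. A reader would see almost no change, or a change of the wrong sign.

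Limits: compare within rows only. Monte Carlo error was not computed. The added reads are applied to all scans from the second on, not just to follow-up scans, which exaggerates the third change. Missed confirmatory scans are not modelled, so the bone rule gets no credit for the events it would properly recover.

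**The case against.** **The other changes are not irrelevant to missing scans.** A reader might infer that only the lifted censoring rule concerns them. The documents do not support that. SAP section 8.1.1 notes that bone progression can occur only up to the scan before the last, so a missed confirmatory scan can remove a bone progression. The COVID-19 sentence also names bone scans explicitly. This stands, and it has a consequence for the remedy: an analysis that lifted only the censoring rule and kept full confirmation would still lose those events.

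**Other outputs give context.** Section 8.2.1 reports how many patients were censored because their event followed two or more missed assessments. If that count is small, the first change cannot have moved the hazard ratio much. The section also tabulates missing assessments by arm, plots scan timing and compares local with central results. Section 6.2 summarizes COVID-19 deviations. So a reader should not infer that nothing planned bears on the question. None of these outputs gives a treatment effect, however.

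**The COVID-19 death analyses are interpretable.** Each can be compared with its own base analysis, and that contrast changes only how COVID-19 deaths are handled. Moving the second to a different base is a preference.

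**These are nominal analyses.** The SAP promises that the impact will be evaluated, not isolated, and a stress test that adds events from several sources has some use. A result close to the primary would be some reassurance. That too stands, but cancellation remains possible.

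**Conclusion.** The point holds, and it is one of interpretation. The difference between the first sensitivity analysis and the primary analysis cannot be attributed to missed scans, because the second and third changes apply whether or not a scan was missed. This follows from the rule definitions and needs no numerical assumption, apart from the reading that scans not centrally read carry site assessments.

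The size in this trial is unknown. The simulated shifts depend on assumed rates, and the opposite-sign result appears only with an assumed imbalance in local calls between arms. A reader might infer from the protocol's background figure, that about 90% of mCRPC patients develop bone metastases, that the bone rule dominates. That figure does not say how often two or more new lesions go unconfirmed from week 16, so it does not support the inference.

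Nor does the point reach the primary rPFS estimate, its alpha or the event count. Section 8.2.1 makes the rPFS sensitivity analyses nominal and without inference, so Type I error is untouched. It is still worth correcting: rPFS is an alternate primary endpoint, the SAP raises the question itself, and the remedy is cheap.

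**What to change.** Keep the first sensitivity analysis as it is. Add one rPFS analysis on the PFS-FAS, with central reads and the primary rules except that:

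1. events count whatever assessments were missed before them; and
2. a Rule 2 bone progression counts without confirmation only when its confirmatory scan was missed, not when that scan was done and did not confirm.

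State in the SAP what makes a confirmatory scan missed, for example that it was due before the data cut-off and was not done. Name this analysis, in place of the first sensitivity analysis, as the evaluation of scans missed because of COVID-19. It covers missed scans from any cause, so where the data allow, also run it restricted to assessments flagged as COVID-19 related under SAP section 6.2. Those categories apply to important deviations, so the flag may be incomplete.

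The cost is one or two extra runs of a modified existing program and a short SAP paragraph. The analysis stays nominal. Separate runs for the bone rule and the added reads, and rebasing the second COVID-19 death analysis, are optional.
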